Individuals who do not qualify for the study due to exclusion criteria #3, 7, or 9, can choose to cease medical cannabis for a 30-day wash-out period (confirm with self-report, PMP and urine drug screen); cease unregulated cannabis, cocaine, opioid, or benzodiazepine use for 30 days (confirmed with self-report and urine drug screen); and/or cease NSAID use for 7 days (self-report). Once they have done this, they can screen for the study again and may be eligible.

Recruitment will occur via Vireo and Montefiore staff referrals. Letters can also be mailed to potential participants in which information will be provided about the study. Flyers will be posted at Vireo dispensary facilities as well as online. We will recruit 3-4 participants per month for 36 months (total sample size of 100). Recruitment will be feasible, as Vireo has over 100 new patients per month. Also, we will utilize the CFAR database to assist with recruitment for this study.

Screening will occur by phone after obtaining oral informed consent. The screening questionnaire will include some questions related to eligibility criteria and others unrelated to eligibility criteria. We will obtain oral consent to review patient's PMP at the same time that we conduct the screening questionnaire. We will schedule eligible participants for a baseline visit and written informed consent will be obtained. In-person screening will occur at Montefiore and Einstein.

Participant tracking. My mentors have extensive experience following populations in studies with follow-up rates of 84%-86% over 6-12 months. At all visits, we will record: 1) participants' address and phone numbers; 2) contact information of family or friends; and 3) locations where participants work or "hang out."

Dispensed opioids or benzodiazepines within 60 d	PR
Non-steroidal anti-inflammatory use within 7 d prior to enrollment	SQ, PR
Steroid use within the past 14 d with duration of therapy ≥ 21 d	SQ, MR
COVID vaccination or booster within 14 days of screening	SQ, MR
SQ=screening questionnaire, MR= medical record, PR=pharmacy records or PMP, TQ=telephone questionnaire; U=urine sample	

Aim	Construct	Measure	Source
Main independent variable			

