In-person visits: Participant's 2 in-person visits will occur in private rooms at the Montefiore/Einstein ICTR Clinical Research Center. At the baseline visit, study staff will describe the study and obtain written informed consent. Tracking forms as well as agreements to release medical, pharmacy, and PMP records will be completed. Participants will receive a refillable debit card for compensation. At all in-person visits, we will administer questionnaires, and collect blood and urine samples. Participants will receive \$27.50 for each in-person visit.

Phone or web visits will occur weekly over 14 weeks and include brief (5-7 minute) questionnaires administered by study staff over the phone or completed on-line. A total of 15 visits will occur, the first at baseline, when participants can be trained on how to complete it, and then one at the end of each week of the follow-up period. Participants will receive \$3 on debit cards after completing each phone or web-based questionnaire.

Blood draws will occur at week 0 and 14 in-person visits. They will measure VL, CD4 count, pro- and anti-inflammatory cytokines. Participants will be compensated an additional \$15 for each visit in which there is a blood draw.

Main independent variable will be the soft gel capsule product dispensed at Vireo, including a 1) high THC capsule, or 2) high CBD capsule. Other key independent variables will be cumulative THC and CBD taken (weeks 3-14, continuous measures).

Main outcome variables: Our primary outcome is pain severity, measured via the BPI severity scale (ordinal variable), as recommended by a committee of international pain experts.⁹² It is an 11-point (0-10) numerical rating scale of pain intensity, where 0 is 'No pain' and 10 is 'Pain as

bad as you can imagine'. Participants will complete the BPI severity scale in each phone visit (baseline and at each weekly visit).

Pro- (TNF α , IL-1 β , IL-6) and *anti-* (IL-4, IL-10) *inflammatory cytokines (secondary outcomes;* 0, 14 week *blood draws*) will be measured with Luminex assay and reported as picograms per mm 3 (continuous measure).

Adverse events (secondary outcomes) will be ARV adherence (AIDS Clinical Trial Group [ACTG] Adherence Interview,^{93,108} Adherence Visual Analog Scale [VAS; weekly]),⁹⁴ VL suppression (blood draws at 0, 14 weeks; copies/mL); and psychological symptoms—depression (CES-D; 0 and 14 weeks),⁹⁵ anxiety (GAD-7; 0 and 14 weeks),^{96,94,97,109}

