Other key outcome variables will be alternative pain measures (painDETECT,⁸⁴ pain catastrophizing⁹⁸).

Other measures that have strong associations with medical cannabis use or neurologic pain will be measured, including biological sex, substance use, quality of life, HIV risk behaviors, symptoms of post-traumatic stress disorder (PTSD), insomnia and medical comorbidities (Table 8).

3) Study Population

3.A. Sample size and power

determination. For our primary analysis (Aim 1), we based our power analysis on proportion of participants with clinically significant change in BPI pain severity scale (30% reduction) in each condition.^{8,48} We will recruit 100 participants in total; we anticipate that approximately 50 will use high THC soft gel

capsules and 50 will use high CBD soft gel capsules. Conservatively assuming 15% attrition in each arm, 42 participants will be in each arm. Because the individual-level intra-class correlation coefficient (ICC) associated with change in pain severity over time is unknown, we conducted simulation studies with varying ICC values, i.e., 0.2, 0.3, and 0.4. We present power calculations for pain severity in Table 9. Based on prior studies,^{47,48} we predict that 40% of those using high THC capsules will experience clinically significant reduction in pain and 20% of those using high CBD capsules will experience clinically significant reduction in pain.¹¹⁰ We will have 84% power at a significance level of 5% (two-tailed test) to detect a 20% difference in proportion of participants who achieve clinically significant reduction in pain during the follow-up period between high THC soft-gel capsules (40%) and high CBD (20%) soft gel capsules. We will have greater power to detect a larger difference or when ICC is lower.

For analyses with continuous dependent variables (Aim 2-3), a sample size of 42 participants/arm will allow us to have >90% power to detect a moderate effect size (i.e., Cohen's $d=0.5$) under a more stringent condition (ICC=0.4). We will have greater power when the effect size is larger or when ICC is lower.

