Aim 1: Examine how medical cannabis use affects self-reported pain. H1: The effect of medical cannabis use on self-reported pain-severity will differ by THC/CBD content. The primary outcome will be change in BPI pain severity scale (ordinal variable, 0-10; measured at baseline and weekly for 14 weeks). A clinically significant change is 30% reduction in BPI pain severity scale.⁹² Secondary measures will include BPI pain interference scale and neuropathic pain (painDETECT). We will compare the proportion of participants who achieve clinically significant change in pain at 14 weeks between those who use high THC soft gel capsules and those who use high CBD soft gel capsules. BPI pain interference scale and painDETECT will be compared between those using high THC vs high CBD as well. We will use mixed-effects logistic regression to test the effect of study arm on pain relief across the course of the study. Results will be adjusted for covariates associated with the outcomes of interest on bivariate testing. We will repeat this model using alternative measures of medical cannabis (cumulative dose of THC and CBD).

Aim 2: Examine how medical cannabis use affects pro- and anti-inflammatory cytokines. H2: Medical cannabis that has higher THC content will have greater reduction in pro-inflammatory

cytokines ($TNF\alpha$, $IL-6$). *H3: Medical cannabis that has higher CBD content will have greater increase in anti-inflammatory cytokines ($IL-4$, $IL-10$).* We will examine how pro- and anti-inflammatory cytokines measured at 0 and 14 weeks change in participants using high THC products versus high CBD products. We will use mixed-effects linear regression analyses to examine intervention and time effects as well as intervention-by-time interactions. This approach is appropriate in the event that the pro- and anti-inflammatory cytokine data show a non-normal distribution. We will repeat this model using alternative measures of medical cannabis (cumulative dose of THC and CBD). We will adjust for other chronic conditions that may lead to change in inflammatory cytokines, such as obesity, cardiovascular disease, and diabetes.

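### Aim 1 responder status at all 14 weekly visits is judged against a single baseline BPI severity rating; a second rating at screening plus baseline adjustment would cheaply add roughly 1 to 5 points of power

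*Combined protocol and SAP*

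**What the plan says.** Section 7.A (Aim 1) defines the outcome: "The primary outcome will be change in BPI pain severity scale (ordinal variable, 0-10; measured at baseline and weekly for 14 weeks". It then sets the responder threshold: "A clinically significant change is 30% reduction in BPI pain severity scale". Two comparisons follow: responder proportions at 14 weeks, and a mixed-effects logistic regression of pain relief over the whole follow-up. Covariates enter if they are associated with the outcome on bivariate testing; baseline BPI is not named.

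Section 2.C gives the schedule: "A total of 15 visits will occur, the first at baseline, when participants can be trained on how to complete it". BPI severity is collected at these weekly contacts. The table of measures lists BPI interference, but not severity, among the in-person questionnaires. No second pre-treatment severity rating and no averaging of baseline ratings is described.

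A screening contact before baseline already exists. Section 2.C says of it: "The screening questionnaire will include some questions related to eligibility criteria and others unrelated to eligibility criteria". Section 4.B allows screening by phone or in person, and Section 2.C allows re-screening after a wash-out.

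**The concern.** A person is a responder in week t if the weekly score Y_t is at or below 0.7 × B, where B is the baseline rating. If B happens to be too high, the person looks like a responder too easily in every week. If B is too low, true relief is missed in every week. Fourteen follow-up ratings average out week-to-week noise in Y_t but leave the error in B untouched. That shared error raises the within-person correlation of the responder calls, which is the ICC that drives Table 9 and which Section 3.A says is unknown. At stake is some avoidable loss of power with 42 evaluable participants per arm.

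**Working it through.** **Inputs from the documents.**
- Section 3.A on rates: "we predict that 40% of those using high THC capsules will experience clinically significant reduction in pain and 20% of those using high CBD capsules".
- Section 3.A on numbers: "Conservatively assuming 15% attrition in each arm, 42 participants will be in each arm".
- Section 3.A on the ICC: "we conducted simulation studies with varying ICC values, i.e., 0.2, 0.3, and 0.4".
- Section 3.A on power: "We will have 84% power at a significance level of 5% (two-tailed test". Table 9 ties this to ICC 0.4.
- One baseline rating and m = 14 weekly ratings (Sections 2.C and 7.A).

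**Step 1: reproduce Table 9.** Effective n per arm = 42 × 14 / (1 + 13 × ICC) = 588 / (1 + 13 × ICC). Power = Φ[(d − 1.96 × SE0) / SE1], with SE0 = √[2p̄(1 − p̄)/n] and SE1 = √{[p1(1 − p1) + p2(1 − p2)]/n}.

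At ICC 0.4, n = 588/6.2 = 94.8, SE0 = √(0.42/94.8) = 0.0666 and SE1 = √(0.40/94.8) = 0.0649. Power = Φ[(0.20 − 0.1304)/0.0649] = 0.858.

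| ICC | n effective | Recomputed, 40% vs 20% | Table 9 |
|---|---|---|---|
| 0.4 | 94.8 | 0.858 | 0.84 |
| 0.3 | 120.0 | 0.927 | 0.91 |
| 0.2 | 163.3 | 0.979 | 0.97 |

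All rows agree within 2 points. One time point with 42 per arm gives only 0.516, so the stated power depends on the repeated calls and hence on the ICC.

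**Step 2: what one baseline contributes.** Responder status depends on Y_t − 0.7B. Assume (the documents do not say) that the baseline rating has the same error variance s² as a weekly one. The shared term is then 0.49s², against s² from each week. On its own it gives a latent correlation of 0.49/1.49 = 0.329. That corresponds to a binary ICC of 0.21 at a 40% rate and 0.18 at 20%, about 0.20 on average.

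**Step 3: average two baseline ratings, independent errors, ICC 0.4.** In an exchangeable latent-normal model, an average binary ICC of 0.4 needs a latent correlation of 0.615.
- Error variance = 1 − 0.615 = 0.385; baseline part = 0.49 × 0.385 = 0.189, which halves to 0.094.
- Total variance falls from 1 to 0.906. Rates become Φ(−0.253/√0.906) = 39.5% and Φ(−0.842/√0.906) = 18.8%.
- Latent correlation becomes (0.615 − 0.094)/0.906 = 0.575, and the average binary ICC about 0.366.
- n = 588/(1 + 13 × 0.366) = 102.1; power = Φ[(0.207 − 1.96 × 0.0636)/0.0619] = 0.908, a gain of 5.0 points.

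The same steps give 0.927 to 0.975 at ICC 0.3 (+4.8) and 0.979 to 0.999 at ICC 0.2 (+2.0, near the ceiling).

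**Step 4: relax the assumptions.**
- Screening and baseline errors correlated 0.3 to 0.5, ICC 0.4: +3.5 to +2.5 points.
- Simulated 0–10 scores with autocorrelated errors: about +1 to +4.
- Only the fall in ICC counted, with 40% and 20% held fixed: about +2.4.
- Week-14 comparison alone: 51.6% to 55.1%, +3.5.

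**Step 5: baseline BPI as a covariate.** Simulated integer 0–10 scores, assuming true baseline mean 5.5 and SD 1.5, SD of fractional response 0.25, and independent rating errors. Power compares person-level responder fractions between arms, with linear adjustment for observed baseline.

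| Rating-error SD | One rating, unadjusted | One rating, adjusted | Two ratings, unadjusted | Two ratings, adjusted |
|---|---|---|---|---|
| 1.0 | 0.814 | 0.824 | 0.85 | 0.854 |
| 1.25 | 0.857 | 0.875 | 0.90 | 0.907 |
| 1.5 | 0.888 | 0.914 | 0.94 | 0.942 |

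Beyond adjustment, the second rating adds 0.030, 0.032 and 0.028: about 3 points, or about 1.5 to 2 if the two errors correlate 0.5.

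**The case against.** One baseline rating contradicts nothing in the plan, and Table 9 already gives 0.84 to 0.97 for 40% vs 20%. The gain rests on SDs and correlations that the documents do not supply. This stands: the point is an efficiency suggestion with a range.

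Four stronger readings are tempting, and the documents do not support them.
- A reader might take 5 points as the expected gain. It is near the top of the range.
- For mean continuous change with independent errors, error variance is s²(1 + 1/14), of which 14/15 = 93% comes from baseline. A second rating gives s²(1/2 + 1/14), a 47% cut. A reader might carry these shares over to the responder analysis. They do not apply there: in the middle simulation the ICC falls only from about 0.41 to 0.38.
- A reader might infer that covariate adjustment cannot help once responders are classified. Given the observed baseline, the cut-off is a known number, and adjustment recovers roughly a quarter to a half of the gain. Section 7.A's bivariate rule might even select baseline BPI, though this is not assured.
- A reader might infer that the baseline rating is made before training. Section 2.C does not give the order.

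Practical objections also stand. Screening is not always by phone, its interval to baseline is not stated, and it runs under oral consent, with written consent only at the baseline visit. No BPI severity threshold governs entry, but a Neuropathic Pain Questionnaire Short Form score above 0 is one entry route, so a same-session BPI rating could run high for people entering that way.

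**Conclusion.** The point holds as a cheap improvement. The error of one baseline rating is shared by all 14 weekly responder calls, and the plan neither averages baseline ratings nor names baseline BPI as a covariate. The gain in Aim 1 power is roughly 1 to 5 points:
- about 4 to 5 with independent errors, no baseline adjustment and an ICC near 0.4;
- about 2 to 3 if the two errors correlate 0.5;
- about 1 to 3 beyond baseline adjustment;
- about 2 at ICC 0.2.

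These figures assume baseline error of the same size as weekly error, response SDs that the documents do not give, and that 40% and 20% are the rates under a single-rating baseline. Every scenario run favoured the second rating, some only slightly.

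**What to change.** In Sections 2.C and 7.A:
1. Add the BPI severity items to the qualifying screening questionnaire, whether by phone or in person. For people who re-screen after a wash-out, use only the qualifying re-screen.
2. Define baseline BPI severity as the mean of that rating and the baseline-visit rating, and compute change and the 30% threshold from this mean.
3. Pre-specify baseline BPI as a covariate in the Aim 1 model. This needs no new data and is worth doing even if item 1 is declined.
4. State that the baseline-visit rating is recorded after questionnaire training.
5. Keep the single-rating definition as a sensitivity analysis.

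The cost is a slightly longer screening, two ratings that may lie days or weeks apart, and a check that the oral screening consent covers using the rating in the primary outcome. The documents do not state enrolment status. If enrolment has begun, the two-rating baseline can apply only to later participants and the gain shrinks accordingly, which is a further reason for item 5.

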The benefits of cannabis may be offset by its adverse events.²⁷ Cannabis is linked to psychological symptoms including anxiety, depression,²⁸ and psychotic symptoms.²⁹ In some studies, cannabis use is associated with poor ARV adherence and virologic failure;³⁰ in others, this is not the case.³¹ No studies have examined how THC/CBD content contributes to adverse events (psychological symptoms, poor ARV adherence, and virologic failure).

Our overarching goal is to test how medical cannabis use affects neuropathic pain, with particular attention to THC/CBD content and adverse events. We propose an observational cohort study of 100 PLWH with (a) neuropathic pain, (b) active certification for medical cannabis, and (c) intent of being dispensed soft-gel capsule products at a medical cannabis dispensary (including high THC: low CBD product and high CBD:low THC product). Over 14 weeks, participants will have 2 in-person visits and 15 phone-based questionnaires (one at baseline, and every week for 14 weeks). Data sources will be blood and urine samples, questionnaires, and medical and pharmacy records. The primary independent variable will be the type of soft-gel capsule product. The secondary independent variable will be reported cumulative THC and CBD dose. The primary outcome will be self-reported pain severity.³² Secondary outcomes will be pro-inflammatory cytokines (TNF α , IL-6), anti-inflammatory cytokines (IL-4, IL-10),¹⁵ psychological symptoms (symptoms of depression,³³ anxiety,³⁴ and psychosis³⁵), ARV adherence, and VL. Among PLWH with neuropathic pain, we will:

Aim 1: Examine how medical cannabis use affects self-reported pain. *H1:* The effect of medical cannabis use on self-reported pain-severity will differ by THC/CBD content.

Aim 2: Examine how medical cannabis use affects pro- and anti-inflammatory cytokines.

H2: Medical cannabis that has higher THC content will have greater reduction in pro-inflammatory cytokines (TNF α , IL-6). *H3:* Medical cannabis that has higher CBD content will have greater increase in anti-inflammatory cytokines (IL-4, IL-10).

Aim 3: Examine how medical cannabis use affects adverse events. *H4:* Participants who use high THC (vs. high CBD) cannabis products will have more psychological symptoms, poorer ARV adherence, and less suppressed VL.

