4. Study records will be kept in locked files and/or within limited access, code-protected computer files, available only to the investigators and study personnel.
5. Publication or presentation of study results will not identify subjects by name.

In addition to addressing issues of confidentiality, it is crucial that we protect participants from emotional distress that may occur during research visits. All visits will occur in medical facilities. If emotional distress occurs during research visits an on-site physician will assess the patient. Per clinical judgment, the participant will either be referred to the Emergency Room or to their treating physicians the following day.

6.C. Potential benefits.

Neuropathic pain in PLWH is associated with poor HIV outcomes, including poor ARV adherence,³² virologic failure,³³ and poor retention in care.^{19,33} PLWH experience a high burden of pain,⁴⁻¹¹ and most commonly experience neuropathic pain.^{12,13} Medical cannabis has known analgesic properties in PLWH with neuropathic pain.^{24,25} Participants in our study will have been evaluated by their own physicians and deemed to be appropriate to receive medical cannabis based on those standards already. By participating in this study, they may experience benefit from medical cannabis use by experiencing improved pain. They may experience increased attention from research staff during the study period, resulting in improved pain, psychological, and HIV outcomes.

7) Data Analysis

7.A Data Analyses: *Intention-to-treat principle* will be used in primary analyses. If key variables (age, sex, medical comorbidities) are unequal among arms, we will conduct adjusted analyses. We will also conduct per-protocol analyses; medical cannabis use for at least 3 months of products will represent sufficient study participation.

Missing data: We will conduct multiple imputations using Markov Chain Monte Carlo imputation methods. Results from multiple imputed data sets will be pooled into a single dataset. We will compare statistical results using datasets with imputed values and the dataset that drops missing values.

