Aim 3: Examine how medical cannabis use affects adverse events. *H4: Participants who use high THC (vs. high CBD) cannabis products will have more psychological symptoms, poorer ARV adherence, and less suppressed VL.* We will examine whether participants using high THC products vs high CBD products have a greater chance of adverse events, including psychological symptoms, ARV adherence, and VL. We will use mixed-effects linear regression analysis for continuous measures (VL, ARV adherence, and psychological symptoms). Each adverse event (Table 8) will be included in a separate model. We will repeat this model using alternative measures of medical cannabis (cumulative dose of THC and CBD).

Aim 4: Explore mechanisms by which medical cannabis promotes analgesia. *H5: Different doses of THC and CBD will have differing effects on inflammatory cytokines, psychological symptoms, and ultimately analgesia.*

We will use a pooled analysis of THC and CBD, using weekly questionnaires and PMP records. We will examine these relationships longitudinally in a stepwise process. First, we will conduct a mixed-effects model to examine how potential mediators lead to analgesia (reduction in BPI severity score). We will repeat analyses for possible mediators, including inflammatory cytokines and psychological symptoms. We will also determine if exposures influence changes in these variables over time, which in turn, influence change in analgesia (e.g., using time-lagged mediators and outcomes). Mediators found to be significant will be included in the final model.⁹² We will calculate the standardized total effect from the exposures to analgesia as well as the standardized mediational (i.e., indirect) effects via mediators. The mediational effect is calculated as the product of the effect from the exposures to the mediators, and the effect from the mediators to the outcome.

8) Data quality control and database management

Data management: Questionnaire, medical records, and PMP data will be de-identified and entered by study staff into a password-protected computer and database. Paper records will be stored in a locked filing cabinet that only research staff can access. Medical and PMP record data will be de-identified and entered in a secure HIPAA compliant web-based system. To protect confidentiality, we will use separate processes for ID- and name-based files and seek a certificate of confidentiality.

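### Product type is not randomised, yet no model for Aims 1 to 3 commits to adjusting for baseline pain, mood or pain treatment; Aim 3 is the most exposed

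*Combined protocol and SAP*

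**What the plan says.** Section 1.A defines the exposure: "The primary independent variable will be the type of soft-gel capsule product". Section 2.A describes an observational cohort in which that product is the one first obtained from the dispensary.

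Section 7.A contains four adjustment rules:

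- **General:** "If key variables (age, sex, medical comorbidities) are unequal among arms, we will conduct adjusted analyses". No criterion for inequality is given.
- **Aim 1:** "Results will be adjusted for covariates associated with the outcomes of interest on bivariate testing". There is no candidate list and no threshold. The aim has two analyses: "We will compare the proportion of participants who achieve clinically significant change in pain at 14 weeks" and "We will use mixed-effects logistic regression to test the effect of study arm on pain relief across the course of the study". The text does not say which of them supplies the data for the screen.
- **Aim 2:** "We will adjust for other chronic conditions that may lead to change in inflammatory cytokines, such as obesity, cardiovascular disease, and diabetes". The model is stated as "We will use mixed-effects linear regression analyses to examine intervention and time effects as well as intervention-by-time interactions".
- **Aim 3:** "We will use mixed-effects linear regression analysis for continuous measures (VL, ARV adherence, and psychological symptoms"), with no covariates and no stated contrast.

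The measures table in section 2.C lists baseline BPI severity, CES-D, GAD-7, pain treatment and comorbidities as collected. It maps measures to aims but does not say what enters a model.

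**The concern.** Without randomisation, product groups may differ at baseline in ways that predict the outcome. Section 1.B itself ties depression and anxiety both to neuropathic pain and to the four study cytokines. Eligibility sets no minimum BPI score, so baseline severity can vary widely. If pain, mood or treatment differs between products, part of each contrast reflects who obtained which product.

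The exposure differs by aim:

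- **Aim 3** falls back on the general trigger, which as written can never bring in pain, mood or pain treatment.
- **Aim 2** adjusts, but not for mood. Its covariates may also fail to reach the contrast of interest, depending on how they are entered.
- **Aim 1** does adjust, but what it adjusts for depends on an unstated threshold.

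**Working it through.** **Plan's own power (section 3.A, Table 9).** Inputs: 42 per arm, 40% v 20%, two-sided 5%, ICC 0.4. With 14 weekly measures, effective n per arm = 42 × 14 / (1 + 13 × 0.4) = 588 / 6.2 = 94.8, which gives 85.8% against the stated 84%. The other five rows also agree within 2 points. Table 9 therefore behaves as a repeated-measures power and is used below as the baseline for cost.

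**Aim 3, unadjusted change contrast.** The documents give no confounder strength. Assume groups 0.5 SD apart on each confounder, each shifting change by 0.2 SD per SD, and no true product effect.

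- One confounder: 0.5 × 0.2 = 0.10 SD.
- Three independent: 3 × 0.10 = 0.30 SD.
- Three correlated at 0.5, each with marginal effect 0.2: the conditional effect is 0.2 / (1 + 2 × 0.5) = 0.1, so bias = 3 × 0.5 × 0.1 = 0.15 SD.

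With 42 per arm, SE = √(2/42) = 0.218 SD. The two-sided rejection rate is Φ(−1.96 + bias/SE) + Φ(−1.96 − bias/SE), which gives about 7%, 28% and 11% in the order above. Simulation gave 7.0%, 27.6% and 10.2%. The independent case falls to about 25% if the confounders' own variance is added to the outcome variance. A fixed set gave 0.00 SD and about 5%.

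**Aim 2, does a main effect reach the contrast?** With both visits present, write Y₁₄ = a + b + (c + d)·product + γX + error and Y₀ = a + c·product + γX + error. In Y₁₄ − Y₀ the term γX cancels, so d, the product-by-time effect, is unchanged by X. In 150 simulated two-visit data sets, the estimates with and without the main effect differed by at most 3 × 10⁻¹⁵. Adding X-by-time removed the bias to within Monte Carlo error (0.078 before; −0.022, SE about 0.017, after).

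**Aim 1, the screen.** Assume 42 per arm, about 30% responders, odds ratio about 1.5 per SD, groups 0.5 SD apart, no product effect. Each person's share of responder weeks was regressed on product, an approximation to the planned mixed logistic model.

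| Analysis | Rule | Spurious difference (points), 3 / 5 independent confounders | False positives |
|---|---|---|---|
| Week 14 | p<0.05 | 4.0 / 6.1 | 7 / 10% |
| Week 14 | p<0.20 | 1.3 / 2.2 | 5 / 5% |
| Week 14 | fixed set | 0.1 / 0.6 | 5 / 5% |
| Weekly, ICC 0.4 | p<0.05 | 1.2 / 2.2 | 6 / 7% |
| Weekly, ICC 0.4 | p<0.20 | 0.3 / 0.7 | 5 / 5% |

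If the ICC is defined as what remains after the confounders, the weekly p<0.05 row becomes about 2-3 points and 6-9%. With three confounders correlated at 0.5, the p<0.05 screen leaves 1.0 point (week 14) or 0.1 (weekly), with about 5% false positives.

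**The case against.** **Aim 1 is adjusted.** The screen sentence directly follows the mixed logistic sentence and most naturally governs the weekly model, where its residual bias is small. This stands. A reader might infer that the primary result would be unadjusted and its error rate grossly inflated. The documents do not support that, because section 7.A says Aim 1 results will be adjusted.

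**The assumed confounding is strong.** Section 1.B describes pain and psychological symptoms as closely linked, so correlated confounders are more plausible than independent ones, and the correlated figures are mild. This also stands. Nor may a reader infer that the groups do differ: the documents do not say how products are chosen.

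**The design already controls some of this.** Eligibility excludes opioids, benzodiazepines and recent NSAID use, and baseline BPI is built into the 30% reduction. Both narrow the problem. But SSRIs, gabapentin, injections and physical therapy remain, and defining an outcome as change does not adjust for baseline differences that predict change.

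**The general rule may add to the others.** It may, but its list omits the three variables at issue, and it is conditional on an undefined inequality.

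**Aim 2's adjustment is not shown to be ineffective.** The cancellation applies only if covariates enter as main effects alone and both visits are present. The plan does not say how they enter.

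**Conclusion.** The concern holds, chiefly for Aim 3, where the written rules allow a product contrast with no adjustment for baseline pain, mood or pain treatment. Under the assumed 0.5 SD separation the bias is 0.10 to 0.30 SD and false positives run from 7% to 28%. For Aim 2 the gap is the absence of mood, pain and treatment, plus the need to state covariate-by-time terms. For Aim 1 the screen is a modest risk: 1 point or less with three correlated confounders, about 1-3 points weekly, and 4-6 points at week 14 with a strict threshold and independent confounders.

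That no model commits to these variables is plain from the text. The size is illustrative and rests entirely on assumed confounder strength. The point is a worthwhile improvement to make before analysis; it does not show that the planned results would be wrong.

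**What to change.** Replace the general trigger and the Aim 1 screen with one prespecified baseline set for Aims 1 to 3, used regardless of p-value or imbalance:

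- baseline BPI severity, CES-D and GAD-7;
- pain treatment in use at baseline, as one yes/no or count variable (records run to week 14, so later treatment must be excluded);
- age and sex;
- medical comorbidities as one count or, for cytokines, the individual conditions listed in full.

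In the CES-D and GAD-7 models, omit the outcome's own week-0 value where it is already a response. For outcomes at weeks 0 and 14, state the product-by-time contrast for Aim 3, as section 7.A does for Aim 2, and enter each covariate with its time interaction. Use the same set in the weekly mixed model for the adherence VAS. Report unadjusted results as secondary.

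For the week-14 responder comparison, expected responders are 0.40 × 42 + 0.20 × 42 = 25.2. Seven covariates plus product gives 25.2 / 8 = 3.2 per coefficient, so enter the set as a single propensity score.

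**Cost.** Only analysis wording changes. Precision was simulated in a linear model, with power = Φ((1.960 + z)/r − 1.960), where z = 0.994 for 84% and r is the SE ratio. Values are for covariates 0 / 0.25 / 0.5 SD apart between groups.

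| Covariates | r | 84% becomes about |
|---|---|---|
| Seven, no prediction | 1.05 / 1.11 / 1.26 | 80 / 76 / 65% |
| Nine, no prediction | 1.064 / 1.131 / 1.333 | 79 / 74 / 60% |
| Six, each 0.2 SD per SD | 0.909 / 0.951 / 1.081 | 90 / 87 / 78% |

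The nine-covariate row shows the price of splitting pain treatment into types. The last row shows that prognostic covariates reduce the loss, or reverse it when groups are similar. For cytokines, nine covariates that predict nothing would take 90% power to about 86 / 82 / 68%.
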